4.7 Discrepant specimens and the Ground Truth

Where there is a discrepancy between the algorithm diagnostic category and pathologist diagnostic category the case will be reviewed by the consensus review team. Discrepancies will be identified by WCTU (see Figure 5 below) by comparing the enrollment data from sites and the COBix classifications of each specimen provided by the TIA Centre and/or Histofy. The WCTU will then forward the details onto the study Research Fellow and consensus group for review.

A minimum of 3 pathologists will decide the correct or ground truth diagnostic category for each slide in the discrepant specimen. If this should require additional laboratory work either in the form of deeper sections, special stains or immunocytochemistry this is requested by from the submitting site.

The consensus view of the study pathologists is the ground truth diagnosis. If this differs from the reference diagnosis, then the PI of the submitting site is informed of the difference, so that this can be brought to the attention of the clinical team. They will then consider if the difference has any impact on management of the patient and take whatever action they deem appropriate.

4.8 Specimen pathway

[figure not shown]

Figure 5 Specimen pathway

4.9 Outcome measures

The study measure is categorisation of diagnosis of a specimen into either normal or abnormal and, secondarily for abnormal specimens, into one of the four abnormal categories listed above. Reference diagnosis category by site pathologists (gold standard) will be compared to COBix algorithm diagnosis category (experimental/intervention) using the following study outcomes.

Primary outcomes: For the validation part of the study, using a pre-specified COBix algorithm threshold, the outcomes will be sensitivity, specificity, negative predictive value (NPV) and positive predictive value (PPV) to detect normal versus abnormal (all categories other than normal including changes of uncertain significance). For all possible COBix algorithm thresholds, the outcomes will be receiver operating characteristic (ROC) and precision-recall (PR) curves.

Secondary outcomes: Agreement on abnormal categories, neoplastic versus non- neoplastic.

Tertiary outcomes: Agreement on urgent versus non-urgent categories (invasive carcinoma and or high-grade dysplasia versus non-invasive neoplasia, and acute inflammation, necrosis, ulceration versus all other pathology).

Additionally, we will use items recorded in clinical details and /or endoscopic findings to reduce the possibility and impact of false negative results from the COBix algorithm and to development the safest possible reporting pathway in practice.

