1. STUDY SUMMARY SCHEMA

Main study

Design: A multi-centre study comparing classification resulting from COBix algorithm with pathologists' reporting of colon biopsy specimens.

Enrolment: 11,000 cases will be enrolled from 11 participating NHS sites (1,000 cases per site).

Primary objective: Comparing classification of normal/ abnormal categories.

Secondary objectives: Comparing classification of into neoplastic urgent/ neoplastic non-urgent/ non-neoplastic urgent/ non-neoplastic non-urgent categories.

Data analysis: Validation of the COBix algorithm by comparing COBix and pathologists' classifications of the same specimens.

Sub study

Health economics: To assess the impact of COBIX algorithm on workflow productivity.

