6. STATISTICAL ANALYSIS

The aim of the study is to validate the COBix diagnostic tool that will be developed before the study begins. We will compute diagnostic measures of sensitivity, specificity, positive predictive value (PPV) and negative predictive value (NPV). The gold standard in the analysis is a pathologist's reference diagnosis. A positive result will be the ability of the COBix diagnostic tool to screen out normal cases. For patient safety, the desire is for the tool to achieve this whilst minimising false negatives and so very high sensitivity and very high NPV are desired. NPV is a function of prevalence of abnormal cases. The prevalence in the study will not be representative because there will be enriching for rare cases (e.g., by ethnicity). However, very high NPV is desired for any case mix. COBix will be considered a good tool if sensitivity and NPV are above 0.98. Specificity will quantify the proportion of normal cases that are screened out and hence the saving in pathologists' workload.

For the cases that are abnormal on both the COBix algorithm and reference diagnosis, based on the categorisation "neoplastic" and "non-neoplastic", we will compute kappa statistic. We will use the kappa statistic to assess agreement between COBix and pathologist diagnosis in categorising abnormal cases as neoplastic or non-neoplastic. Also, taking the gold standard as a pathologist's categorisation of an abnormal case as neoplastic or non-neoplastic, we will compute sensitivity, specificity, and other diagnostic measures.

For the cases that are abnormal on both the COBix algorithm and reference diagnosis, based on the categorisation "urgent" and "non-urgent", we will compute kappa statistic. We will use this kappa statistic to assess agreement between COBix and pathologist diagnosis in categorising an abnormal case as urgent or non-urgent. Also, taking a pathologist's reference diagnoses as the gold standard, we will compute sensitivity, specificity, and other diagnostic measures. Comparison of categorisation as urgent and non-urgent will be based on all abnormal cases and in subgroup analyses of separately analysing neoplastic cases and non-neoplastic cases.

Subgroup analysis will repeat the above set of analyses for clinically important patient subgroups such as categories based on sex, ethnicity, age and site of the biopsy.

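### The four-category secondary objective in section 1 is assessed only in components: no named outcome gives joint four-category agreement, and urgency is ranked differently in section 1 and section 4.9

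*Protocol*

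**What the plan says.** Protocol section 1 gives the secondary objective as "Comparing classification of into neoplastic urgent/ neoplastic non-urgent/ non-neoplastic urgent/ non-neoplastic non-urgent categories". Section 4.9 opens in the same way: the study measure places specimens as normal or abnormal and, "secondarily for abnormal specimens, into one of the four abnormal categories listed above".

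The outcomes that section 4.9 then names are two binary ones. The first is "Secondary outcomes: Agreement on abnormal categories, neoplastic versus non- neoplastic". The second, ranked tertiary, is agreement on urgent versus non-urgent, with urgency defined separately for neoplastic and for other pathology.

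Section 6 restricts both comparisons to cases abnormal on COBix and on the reference. One kappa is to "assess agreement between COBix and pathologist diagnosis in categorising abnormal cases as neoplastic or non-neoplastic". The other is to "assess agreement between COBix and pathologist diagnosis in categorising an abnormal case as urgent or non-urgent". Sensitivity, specificity and other diagnostic measures accompany each. The urgency comparison is made in all abnormal cases and again separately in neoplastic and in non-neoplastic cases. Section 6 does not say whether those groups are formed by the reference, by COBix or by both.

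Under section 4.5, the pathologist and COBix each assign every specimen to one of five categories.

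**The concern.** The objective asks about joint placement, but the outcomes look at one axis at a time. A neoplastic urgent specimen that COBix calls non-neoplastic urgent is an agreement in the overall urgency table. It is a disagreement in the neoplastic table, but there it is pooled with other neoplastic errors, such as a neoplastic non-urgent specimen called non-neoplastic urgent. The proportion of neoplastic urgent specimens placed in exactly the right category is not a named result.

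The tiers also conflict. Urgency is part of the secondary objective in section 1 and tertiary in section 4.9. At stake is whether the report answers the secondary objective as written, and at which rank urgency results are to be read.

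**Working it through.** The protocol states no figure for these agreements, so there is none to reproduce. The question is whether the analyses named in section 6 determine four-category agreement. All counts below are assumed for illustration and refer to specimens abnormal on both raters.

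**Bounds.** If agreement is a on one axis and b on the other, exact four-category agreement lies between a + b − 1 and min(a, b).
- At 95% on each axis: 0.95 + 0.95 − 1 = 0.90, up to 0.95.
- At 90% on each axis: 0.80 up to 0.90.

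**Example 1.** There are 1,000 specimens, with reference counts of 150 neoplastic urgent (NU), 450 neoplastic non-urgent (NN), 150 non-neoplastic urgent (nU) and 250 non-neoplastic non-urgent (nN).
- Table J: 5% of each row is wrong on both axes at once.
- Table S: 5% of each row is wrong on the neoplastic axis only, and another 5% on the urgency axis only.

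Both collapse to the same two-by-two tables (rows reference, columns COBix):
- Neoplastic axis: [570, 30; 20, 380]
- Urgency axis: [285, 15; 35, 665]

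Kappa = (po − pe)/(1 − pe), where po is observed and pe is chance agreement.
- Neoplastic: pe = 0.60×0.59 + 0.40×0.41 = 0.518; kappa = (0.95 − 0.518)/0.482 = 0.896 in both.
- Urgency: pe = 0.30×0.32 + 0.70×0.68 = 0.572; kappa = (0.95 − 0.572)/0.428 = 0.883 in both.
- Four categories, J: agreement 950/1,000; pe = 0.305; kappa = 0.645/0.695 = 0.928.
- Four categories, S: agreement 900/1,000; pe = 0.303; kappa = 0.597/0.697 = 0.857.

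**Urgency subgroups of section 6, by how they are formed.**

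| Basis | Neoplastic kappa, J / S | Non-neoplastic kappa, J / S |
|---|---|---|
| Reference | 0.871 / 0.871 | 0.894 / 0.894 |
| COBix | 0.912 / 0.870 | 0.846 / 0.896 |
| Both raters agree | 1.000 / 0.864 | 1.000 / 0.889 |

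- *Reference basis.* The subgroup tables are identical cell by cell, so sensitivity and specificity match as well as kappa. Nothing named in section 6 separates J from S.
- *COBix basis.* These two tables happen to be separated. Kappa is unchanged when rows and columns are swapped, so the transposes of J and S would not be.
- *Both agree.* Exact agreement is the sum of the subgroup diagonals: J 142.5 + 427.5 + 142.5 + 237.5 = 950; S 135 + 405 + 135 + 225 = 900. The four-category kappa also needs the margins, which depend on where specimens discordant on neoplastic status fell, so in general it is not fixed.

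**Example 2, the most serious category.** There are 1,500 specimens, with reference counts NU 300, NN 500, nU 400 and nN 300. All specimens are placed correctly except:
- Table A: 50 NU called nU, and 50 NN called NU.
- Table B: 50 NN called nU.

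Both give kappa 0.933 on each axis. With reference-based subgroups, both give 0.871 (neoplastic) and 1.000 (non-neoplastic). Exact placement of NU is 250/300 = 83.3% in A and 300/300 = 100% in B. Four-category agreement and kappa are 1,400/1,500 = 93.3% and 0.910 in A, and 1,450/1,500 = 96.7% and 0.955 in B. If both raters must agree on neoplastic status, the neoplastic subgroup kappa is 0.857 in A and 1.000 in B, so that basis does separate them.

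**The case against.** The four categories are simply the two axes crossed. Section 6 analyses both axes and repeats urgency within each neoplastic group, and section 4.9 defines urgency separately for each. That is a hierarchical analysis of the same classification. Section 6 limits its comparisons to cases abnormal on both raters, so reading the subgroups as neoplastic on both is natural, and on that reading percent agreement is recoverable. All of this stands. A reader might infer that the objective is never measured, or that the extra error shows in no planned kappa; the documents do not support either.

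Nor is a neoplastic urgent specimen called non-neoplastic urgent hidden. It counts against COBix on the higher-ranked neoplastic outcome, and the category difference sends it to consensus review under section 4.7. That also stands, although the review settles individual specimens and is not an agreement outcome.

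An unweighted four-category kappa is no better in itself than the axis measures. In example 1 it favours table J, where every error lands in the diagonally opposite category, and both tables call 15 of 300 urgent specimens non-urgent. This is a reason to keep the axis measures and show the whole table, not to leave the joint result out.

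Finally, an extra table and the subgroup basis could sit in a SAP that is not shown. That is fair for those details. It does not cover the conflict between section 1 and section 4.9, which lies within the protocol.

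**Conclusion.** The point holds in a limited form. The secondary objective is assessed in components, no named outcome gives joint four-category agreement, the basis of the urgency subgroups is unstated, and urgency has two different ranks.

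The size depends on the unstated basis. With reference-based subgroups, identical planned results are compatible with 95% or 90% exact agreement in example 1, and with 83.3% or 100% exact placement of neoplastic urgent specimens in example 2. If both raters must agree on neoplastic status, the gap narrows to the four-category kappa. The category mixes and error rates are assumptions, chosen to show what the planned analyses can and cannot distinguish; they do not predict COBix performance.

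The only stated performance criterion, sensitivity and NPV above 0.98 for normal versus abnormal, does not depend on any of this. The change is worth making but does not threaten the primary result.

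**What to change.** In sections 4.9 and 6:
- Name as the secondary outcome the cross-tabulation of reference against COBix over the four abnormal categories, with the COBix-normal column shown.
- Report from it the proportion of each reference category placed in exactly the right category, and a four-category kappa with its interval.
- Keep the neoplastic and urgency comparisons as components.
- State whether the urgency subgroups are formed by the reference, by COBix or by both.
- Give urgency the same secondary or tertiary rank in section 1 and section 4.9.

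The cost is one extra table and one kappa from categories already recorded for every specimen. The reported agreement may look slightly less favourable than the single-axis figures.

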5. TRAINING

Site initiation

Each site will have a site initiation where the Principal Investigator and their team participate in an induction session. This was carried out over video conference.

A checklist will be completed for all sites to confirm that pre-activation activities are completed. Support is offered by relevant study team members to staff at participating sites to ensure they remain fully aware of study procedures and requirements. Working instructions will be provided for technical staff and pathologists. Additional support and training is offered to sites where necessary.

6. STATISTICAL ANALYSIS

The aim of the study is to validate the COBix diagnostic tool that will be developed before the study begins. We will compute diagnostic measures of sensitivity, specificity, positive predictive value (PPV) and negative predictive value (NPV). The gold standard in the analysis is a pathologist's reference diagnosis. A positive result will be the ability of the COBix diagnostic tool to screen out normal cases. For patient safety, the desire is for the tool to achieve this whilst minimising false negatives and so very high sensitivity and very high NPV are desired. NPV is a function of prevalence of abnormal cases. The prevalence in the study will not be representative because there will be enriching for rare cases (e.g., by ethnicity). However, very high NPV is desired for any case mix. COBix will be considered a good tool if sensitivity and NPV are above 0.98. Specificity will quantify the proportion of normal cases that are screened out and hence the saving in pathologists' workload.

For the cases that are abnormal on both the COBix algorithm and reference diagnosis, based on the categorisation "neoplastic" and "non-neoplastic", we will compute kappa statistic. We will use the kappa statistic to assess agreement between COBix and pathologist diagnosis in categorising abnormal cases as neoplastic or non-neoplastic. Also, taking the gold standard as a pathologist's categorisation of an abnormal case as neoplastic or non-neoplastic, we will compute sensitivity, specificity, and other diagnostic measures.

For the cases that are abnormal on both the COBix algorithm and reference diagnosis, based on the categorisation "urgent" and "non-urgent", we will compute kappa statistic. We will use this kappa statistic to assess agreement between COBix and pathologist diagnosis in categorising an abnormal case as urgent or non-urgent. Also, taking a pathologist's reference diagnoses as the gold standard, we will compute sensitivity, specificity, and other diagnostic measures. Comparison of categorisation as urgent and non-urgent will be based on all abnormal cases and in subgroup analyses of separately analysing neoplastic cases and non-neoplastic cases.

Subgroup analysis will repeat the above set of analyses for clinically important patient subgroups such as categories based on sex, ethnicity, age and site of the biopsy.

The validation part of the study that corresponds to the analysis described above will be based on a pre-specified COBix algorithm threshold obtained using external data. Additional analysis will consider diagnostic ability of all COBix algorithm predictive scores and so we will perform ROC curve analysis and PR curve analysis.

The performance of the predictive algorithm will be determined by Warwick Clinical Trials Unit (WCTU) using the reference diagnosis received from different sites and the class-wise prediction scores generated by different variants of the predictive algorithm.

An interim analysis is planned around month 18. The study will stop for futility if sensitivity/NPV is below a pre-specified value. The exact time for the interim analysis and the exact value of futility value will be pre-determined by the Study Steering Committee (SSC). The final analysis will adjust for the possibility of stopping for futility at interim analysis. A detailed and comprehensive statistical analysis plan (SAP), that will include how the final analysis will adjust for the possibility of stopping for futility, will be written and approved before performing the interim analysis.

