4.5 Study size, case selection and case enrolment

The study will enrol 11,000 cases. Sample size for the analysis corresponds to the number of specimens and on average, it is expected that each case will have three specimens. In assessing sample size adequacy, we were conservative assuming that there will be one specimen per case, rather than the expected average of three per case. A sample size of 11,000 is adequate to estimate diagnostic measures (sensitivity, specificity, negative predictive value (NPV) and positive predictive value (PPV)) with high precision if the study will have a positive finding of obtaining sensitivity and NPV values of at least 0.98. Assuming we will observe NPV=0.98 and same number of normal cases by pathologists and COBix algorithm, varying prevalence between 49% and 90% (observed data in seven sites in Table 1), the largest margin of error (1.96 x standard error) for any of the four diagnostic measures is 0.02 so that confidence intervals for all diagnostic measures will be very narrow. This sample size may seem large, but it is essential to deliver comprehensive assessment of the tool across all patient groups and the full range of pathological entities encountered in practice.

The study has been designed with the majority of cases (9,900) coming from retrospective cases, with 1,100 cases being recruited prospectively. Using retrospective cases is appropriate in this setting and ensures the volume of cases can be recruited and examined in the time available. It also ensures rare and unusual entities can be included so we can explore how these are handled by the algorithm. Prospectively recruited cases will be selected sequentially and will allow the study to collect health economics data, including the time taken for pathologists to examine normal biopsies and the broader impact on pathology workflow.

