Selected cases are recruited and the specimen reviewed by the study pathologist for enrollment. The specimens are anonymised at the point of enrollment. The anonymisation process provides a unique case number, a part identifier, a block identifier and a slide identifying number. Where multiple specimens are combined into one block and all appear on one slide the process for anonymization and number is the same, but the slide receives multiple numbers to account for each specimen it contains. The fact that it is a multi-specimen slide is annotated in the study database. The orientation of the WSI will be used to segment the WSI into the component parts prior to the slide being processed through COBix.

At the point of review, the study pathologist provides the diagnosis of each specimen in the case under the anonymized number on the study database. This is the **reference classification and diagnosis**. All cases are therefore enrolled with two pathologist reviews: the reporting pathologist and the study pathologist. These may be the same person. The timings for the health economics study are taken on the first review only.

To ensure representation from all ethnic groups, case selection will be divided between racial groups in the following proportions:

- White Caucasian groups 70%;
- Black, Asian and minority ethnic (BAME) groups, including racial group unknown 30%.

Prospective cases

Each site enrolls one hundred sequential large bowel biopsy cases prospectively after the study starts.

Retrospective cases

Nine hundred cases are enrolled from the pathology archives at each site. Of these 100 cases is reserved for the categories of rare and unusual diagnoses. The remaining 800 cases are collected sequentially from a time period chosen by the enrolling site.

Classification of specimens

At enrolment, each specimen is classified by the recruiting pathologist into one of the categories shown below:

Diagnostic categories

- 1) **Normal** (any specimen which contains no evidence of disease)
- 2) **Non-neoplastic non-urgent** (any non-neoplastic abnormality which does not have acute inflammation - necrosis or ulceration)
- 3) **Non-neoplastic urgent** (any non-neoplastic abnormality which includes either acute inflammation or necrosis or ulceration)
- 4) **Neoplastic – non-urgent** (any neoplastic lesion which does not include either invasive carcinoma or other form of malignancy or high-grade dysplasia)

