- 5) **Neoplastic urgent** (any neoplastic lesion which includes either high grade dysplasia or invasive carcinoma or other malignant diagnosis)

These categories match then the classification tree in figure 4.

All H&E slides from a case will be seen by the algorithm, but diagnostic categorisation will be done at the specimen level within a case.

[figure not shown]

Figure 4 is a schematic diagram of the COBIx biopsy classification tree depicting how specimens will be classified in the study.

Both pathologists and COBIx classifies each specimen enrolled into one of the five diagnostic categories shown.

Case selection

Each site collects 1000 cases for the study in the following manner:

First, a search of the pathology archive for any of the diagnoses of interest (Cases of interest) listed below of any age and as many of these cases as can be found number X.

Second, a series of cases 900-X from any time period prior to August 2023 using an enrichment process to ensure 30% of cases come from minority ethnic groups, remaining cases are collected sequentially.

Third, a series of 100 cases collected during the trial period to be arranged with the coordinating centre.

Cases of interest, and other interesting and educational cases discovered during the course of the study, will be configured into a training set for the RCPATH Portal.

For the cases enrolled into this study the site will review and ascertain the diagnosis of each specimen and categorise this into one of the 5 categories using the definitions provided.

This work is to be supervised by the principal investigator for the site, the work may be delegate to other staff (trainee pathologists, biomedical scientists, medical students etc. providing they have sufficient training and knowledge and are adequately supervised in this work) as appropriate.

Inclusion criteria

Large bowel endoscopic biopsies from adult patients (over 18 years)

Exclusion criteria

Specimens which are not from large bowel endoscopic biopsies

Incomplete cases with lost slides

Cases from person opting out via the NHS Data opt-out scheme

Faded or damaged slides

Incomplete or missing meta data

The following metadata is required for each case:

Site code

Laboratory number

Ethnic group

Gender

Age group

Procedure type

Tissue Type

Date of biopsy

Colonoscopy report

Clinical details

Specimen parts

Specimen blocks

Macroscopic report

Microscopic report

Diagnosis

SNOMED Code

Scanner type

Image resolution

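### The 0.98 limit on NPV has no reference prevalence, and the rare-case enrichment is given two different sizes, so the verdict depends on case mix as well as on the algorithm

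*Protocol*

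**What the plan says.** **Pass rule.** Under Protocol section 6, COBix "will be considered a good tool if sensitivity and NPV are above 0.98". The same paragraph notes that NPV is a function of the prevalence of abnormality. It continues: "The prevalence in the study will not be representative because there will be enriching for rare cases". Its response is that "very high NPV is desired for any case mix". It gives no reference prevalence, and no confidence bound accompanies the limit.

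**What counts as positive.** The opening of section 4.5 calls 11,000 adequate "if the study will have a positive finding of obtaining sensitivity and NPV values of at least 0.98", and works out precision assuming that an NPV of 0.98 is observed.

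**Enrichment, first statement.** Section 4.5, Retrospective cases, allots 900 archive cases per site: "Of these 100 cases is reserved for the categories of rare and unusual diagnoses". The other 800 are sequential.

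**Enrichment, second statement.** Section 4.5, Case selection, has each site search first for the listed diagnoses and take "as many of these cases as can be found number X". It then fills up with 900-X cases, which are themselves enriched by ethnicity. No cap on X is given.

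**The concern.** The two statements agree only when X is 100. Sites select cases under the protocol, so a later analysis plan cannot settle which instruction they followed.

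The pass rule inherits this ambiguity. NPV falls as prevalence rises, even when the algorithm's behaviour on each kind of specimen is unchanged. A single NPV limit without a stated prevalence is therefore a moving bar. Wanting high NPV in every case mix is an aim, and one NPV from one mix does not test it.

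A pass is meant to support automated normal reports that a pathologist would not routinely see (section 4.2), and the study is to supply the efficacy and safety data for regulatory approval (section 4.1). A pass might not carry over to a site with more disease, and a fail might partly reflect how many rare cases the archives held.

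**Working it through.** **Inputs from the protocol.** N is 11,000, treated as one specimen per case (section 4.5). Table 1 gives 27% to 50.7% normal across sites and 34.5% pooled, so abnormal prevalence p runs from 49.3% to 73%, with 65.5% pooled. The unweighted mean of the seven sites is 37.5% normal, so p = 62.5%.

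**Assumptions.** The protocol gives no specificity or rare-case sensitivity. I take specificity 0.90 and show other values where they matter.

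**1. The plan's own figure.** With NPV 0.98 and equal numbers called normal by both readers, specificity is also 0.98. The margin for both is 1.96 × √(0.98 × 0.02 / number of normals).
- At 90% abnormal (1,100 normals) it is 0.0083.
- At 73% (2,970 normals) it is 0.0050.
- The stated largest margin of 0.02 is a safe upper limit but is not reproduced. The 90% prevalence credited to Table 1 is not there either; the table's highest value is 73%.

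**2. NPV across Table 1.** NPV = spec(1-p) / [spec(1-p) + (1-sens)p], with sensitivity 0.99:

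| Abnormal | spec 0.80 | spec 0.90 | spec 0.98 |
|---|---|---|---|
| 49.3% | 0.988 | 0.989 | 0.990 |
| 62.5% | 0.980 (0.9796) | 0.982 | 0.983 |
| 65.5% | 0.977 | 0.979 | 0.981 |
| 73% | 0.967 | 0.971 | 0.973 |

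At specificity 0.90 the verdict already differs between the equal-site mean and the pooled mean.

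**3. The sensitivity actually required.** NPV of 0.98 needs sens = 1 - (0.02/0.98) × spec × (1-p)/p. At specificity 0.90 this is 0.981 at 49.3%, 0.990 at 65.5% and 0.993 at 73%. Even with specificity 1, the required sensitivity exceeds 0.98 once p is above 1/1.98 = 50.5%. Above that prevalence the NPV limit implies the sensitivity limit.

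**4. Effect of X with equal sensitivity.** Count every enriched specimen as abnormal, so p = 0.655(1-f) + f with f = X/1000. Specificity is 0.90.

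| X | p | NPV, sens 0.991 | NPV, sens 0.992 |
|---|---|---|---|
| 0 | 0.655 | 0.981 | 0.983 |
| 100 | 0.690 | 0.978 | 0.981 |
| 200 | 0.724 | 0.974 | 0.977 |

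**5. How far step 4 depends on its assumptions.**
- If rare cases are harder (0.995 routine, 0.95 rare), NPV goes from 0.990 at X = 0 to 0.972 at X = 100. With 0.98 in rare cases it is 0.983 at X = 100, a pass.
- Suppose one of three specimens in an enriched case is the rare lesion and the other two follow the routine mix. Such a case is then (1 + 2 × 0.655)/3 = 77.0% abnormal, and p at X = 100 is 0.9 × 0.655 + 0.1 × 0.770 = 0.6665. With sensitivity 0.991, NPV is 0.980 (0.9804), just a pass.

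**6. Point estimate.** With 11,000 × 0.345 = 3,795 algorithm-normal specimens, exact binomial, the chance that the estimate exceeds 0.98 is 49% at a true NPV of 0.980 and 19% at 0.978. On 11,385 independent specimens (three per case) the second figure is 7%.

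**The case against.** **Enrichment.** The two statements coincide at X = 100. They can be read together as 100 reserved places filled with whatever is found, and nothing suggests that an archive yields hundreds. That is a fair reading, but the second statement sets no ceiling and nothing says that the first overrides it. The wording still has to be reconciled.

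**Point estimate.** The protocol never says that the limit applies to observed values, and an analysis plan could add a bound. This stands as a caveat. The inference rests on section 4.5, which treats obtaining 0.98 as positive and sizes the study on observing exactly that; a lower confidence limit at that value lies below 0.98.

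**Size of the swing.** A large effect of enrichment needs markedly lower sensitivity in rare cases, and failing a tool that misses rare disease is a finding about the tool. That is right. The case rests on steps 2 and 4, where the effect is a few thousandths to about two hundredths of NPV.

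**Recoverability.** Sensitivity and specificity are primary outcomes, so NPV at any prevalence can be derived later. True, but the pass rule must say which NPV it judges.

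**Stronger readings to avoid.**
- A reader might infer that any tool at the safety limit passes half the time. This holds for the NPV limb only: at 65.5% abnormal, sensitivity 0.98 with specificity 0.90 gives NPV 0.960, which essentially never passes.
- A reader might infer that futility is judged on the same pooled sample, with rare cases making up 100/450 = 22% of it against 10% at the end. The protocol says only "The study will stop for futility if sensitivity/NPV is below a pre-specified value", leaves value and timing to the steering committee, and does not say that the selection list is the enrolment order. The 22% is conditional on both points and is not part of this finding.

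**Conclusion.** The point holds in this form. The protocol contradicts itself on the size of the rare-case enrichment. It also fixes an NPV limit without a reference prevalence while conceding that the study's prevalence is unrepresentative.

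Across Table 1 the same tool (sensitivity 0.99, assumed specificity 0.90) moves from NPV 0.989 to 0.971 and crosses the limit on the way. Moving X from 0 to 100 costs about 0.003 of NPV at equal sensitivity. That is enough to change the verdict for a tool near the limit. The cost is larger if rare cases are harder to detect and smaller if only some specimens of an enriched case are abnormal. Chance matters only close to 0.98, and that part rests on the point-estimate reading. The binomial figures assume independent specimens; the protocol gives no within-case correlation.

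The documents do not show that enrichment alone would fail a sound tool by a wide margin.

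**What to change.** 1. Reconcile the two statements in section 4.5 to one number, or one cap, of cases of interest per site.
2. For the pass rule, compute NPV from sensitivity and specificity in the sequential series at a stated reference prevalence, for example 65.5%, and tabulate it at 49% and 73%. Report sensitivity in the cases of interest separately and alongside, so that missed rare disease stays visible. Reweighting for the ethnic enrichment is possible only if target proportions are specified; the protocol gives none.
3. Require the lower two-sided 95% confidence limit, allowing for several specimens per case, to exceed 0.98. Use one wording of the limit: section 6 has above, section 4.5 has at least.

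**Cost.** Protocol and analysis-plan wording, and no extra cases. With X = 100 the NPV estimate would use 900 of 1,000 cases per site. The observed NPV needed to pass rises to roughly 0.985 (3,737 of 3,795) or 0.983 (11,187 of 11,385) if specimens are independent; a standardised, clustered estimate would differ somewhat. On 3,795 specimens the chance of clearing the NPV limb becomes about 2% at a true NPV of 0.98, 59% at 0.985 and over 99% at 0.99.
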